1.2 Study Rationale and Study Design

This randomized, controlled trial (see Schema) is designed to evaluate the effect of acupuncture on CIPN, other symptoms, and potential opioid and concomitant medication sparing effects in comparison to standard of care management in MM subjects. We hypothesize that acupuncture will be associated with: 1) a clinically significant and statistically significant reduction in CIPN; 2) statistically significant reduction of other symptoms such as nervousness and lack of energy; and 3) statistically significantly improved QOL at ten weeks. We also theorize that acupuncture will be opioid and concomitant medication sparing at ten weeks. We expect that the dose of acupuncture received will impact the outcomes, with higher doses of acupuncture being associated with better outcomes.

This study is novel in that it will be, to our knowledge, 1) the largest randomized, controlled trial to examine the effect of acupuncture on CIPN in MM patients 2) the first to explore the impact of acupuncture on opioid and concomitant medication intake.

This project aims to strengthen the care of persons with MM by improving quality of life (QOL) and ability to perform daily activities through reduced CIPN symptoms. CIPN debilitates and erodes QOL by preventing individuals from pursuing their normal activities of daily living. The features of CIPN, including physical, social/family, emotional, functional, and specific CIPN

symptoms, will be measured with the validated FACT-GOG-NTX.⁵⁸ This project brings necessary attention and scientific inquiry to supportive cancer care, which is sometimes de-prioritized behind disease treatment.^{59,60} The potential for nonpharmacologic acupuncture to reduce CIPN and other symptoms with minimal side effects has beneficial implications for disease treatment. Patients with controlled symptoms are better able to tolerate life-prolonging treatment and avoid chemotherapy dose reductions which result from neurotoxic side effects of chemotherapy.^{11,61,62}

African Americans are twice as likely to develop MM compared to Caucasians,^{63,64} yet are less likely to receive supportive care to address side effects and QOL issues.^{65,66} At Levine Cancer Institute, approximately one-third of MM patients are African American. Acupuncture can strengthen the care of persons with MM by supporting their treatment and improving QOL. This study may promote health equity by treating a marginalized population. While there is not an aim to examine disparities, it is important to highlight the vulnerability of the population.

Subjects will be referred from myeloma, palliative or supportive oncology clinics at Levine Cancer Institute. Subjects who consent and are determined to be eligible will be randomized to receive either acupuncture treatment or standard of care treatment for their CIPN. Subjects' sociodemographics, medical history, opioid and concomitant medication intake information will be collected. Subjects who are randomized to the acupuncture treatment arm will receive 12 sessions of acupuncture over approximately 10 weeks and their CIPN will continue to be treated by their physician. Subjects randomized to standard of care will continue only with standard of care therapy per their physician for treatment of their CIPN. All subjects will complete questionnaires at Baseline, midpoint, and endpoint. Responses to questionnaires will then be analyzed towards answering the study's objectives.

2. STUDY OBJECTIVES

2.1 Objectives

2.1.1 Primary Objective

- The primary objective of this study is to evaluate the effectiveness of acupuncture plus standard subject management versus standard subject management in terms of reduction of neuropathy in multiple myeloma subjects actively treated with bortezomib diagnosed with CIPN or multiple myeloma subjects who have discontinued bortezomib within the past 12 months but continue to have CIPN (even if they have started new therapy that could cause neuropathy). Neuropathy will be subject reported using an 11-point scale from 0-no neuropathy to 10-worst possible neuropathy.

2.1.2 Secondary Objectives

- To compare subjects with and without acupuncture for the following symptoms assessed by the FACT-GOG-NTX questionnaire:
 - Specific features of CIPN utilizing the NTX sub-scale (e.g. numbness, tingling)
 - Nausea

- Sadness
- Nervousness
- Sleep quality
- Lack of energy
- Pain

- To compare subjects with and without acupuncture for the following symptoms assessed by an adaptation of the FACT-GOG-NTX questionnaire:
 - Constipation
 - Dizziness
 - Dry mouth.
- To compare Quality of Life in subjects with and without acupuncture using the CDC HRQoL-4 questionnaire.

2.1.3 Safety Objective

- To summarize adverse events of special interest for subjects receiving acupuncture intervention

2.1.4 Exploratory Objectives

- Exploratory objectives are to compare subject with and without acupuncture for:
 - Opioid use, defined by Morphine Equivalent Daily Dose (MEDD)¹
 - Concomitant medication use, including gabapentin, duloxetine, pregabalin, etc.
- To evaluate whether there is a dose response based on the amount of acupuncture delivered, defined by the number of attended acupuncture sessions from 0 to 12, for subjects randomized to the acupuncture arm.
- To evaluate the effect of acupuncture expectancy for subjects receiving acupuncture intervention

3. SUBJECT SELECTION

3.1 Subject Identification and Recruitment

Adult subjects will be recruited at Levine Cancer Institute (LCI). Subjects will be recruited regardless of their sex, race, and ethnicity.

3.2 Inclusion Criteria

Subject must meet all the following applicable inclusion criteria to participate in this study:

1. Written informed consent and HIPAA authorization for release of personal health information. **NOTE:** HIPAA authorization may be included in the informed consent or obtained separately.

2. Age \geq 18 years at the time of consent
3. Subject has diagnosis of Multiple Myeloma (any stage)
4. Currently being treated with bortezomib or bortezomib-combination chemotherapy OR subjects who have discontinued bortezomib within the past 12 months but continue to have CIPN (even if they have started new therapy that could cause neuropathy)
5. ECOG Performance status of 0-3
6. Life expectancy of \geq 12 weeks
7. Subject-reported Neuropathy score of \geq 2
8. No planned hospital admission within the expected time frame of study participation. For potential participants with a transplant in their current MM treatment plan: Post-transplant subjects may enroll when recovered sufficiently from the transplant, i.e. platelets $>50 \times 10^3/\mu\text{L}$, ANC $> 0.5 \times 10^3/\mu\text{L}$, and ECOG performance status is 0-3.
9. As determined by the enrolling physician, ability of the subject to understand and comply with study procedures for the entire length of the study

3.3 Exclusion Criteria

Subjects meeting any of the criteria below may not participate in the study:

1. Uncontrolled intercurrent illness/medical condition or psychiatric illness/social situations that would limit compliance with study requirements as determined by the investigator
2. Subjects with neuropathy pain as a result of any other cause other than chemotherapy
3. Subjects with needle phobia
4. Previous diagnosis of amyloidosis or POEMS syndrome
5. Documented local infection at or near the planned acupuncture sites (see Appendix A) as determined by the enrolling investigator
6. Subjects with metastatic involvement of the nervous system/active central nervous system disease
7. Plan to receive Healing Touch or Oncology Massage during study
8. Have received acupuncture within 30 days prior to enrollment

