4. SUBJECT ALLOCATION

4.1 Randomization

Subjects will be randomized in a 2:1 fashion to either acupuncture plus standard subject management or standard of care alone and assigned a Sequence Number. This will be accomplished utilizing the CTMS, whereby a list of Sequence Numbers and associated treatment arm assignments randomly generated prior to study activation will be uploaded by a member of the Levine Cancer Institute Biostatistics Core. The Sequence Number will be a four digit, randomly generated ID number, ranging from 0001 to 9999. A stratified block randomization will be utilized including the following stratification factors to reduce confounding of comparisons between the treatment arms:

- Baseline neuropathy score (neuropathy score 2 – 6 vs 7 – 10)

Blinding will not be possible within this trial because the subjects and study personnel will be able to decipher intervention from control based on the study activities. Those exposed to acupuncture will understand that they are in the intervention group and those given standard of care only will understand that they are in the control group. If a subject in the control group has an acupuncture session while enrolled, they will be discontinued from the study and all further assessments at that point.

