6. STUDY CALENDAR

Procedures/Assessments	Screening Visit	Baseline (complete within 2 weeks from consent, can be done at screening AFTER Randomization)	Weeks 1-2 ² : Twice per week	Weeks 3-10 ² : Once per week	Week 5 ± 1 week ^{3,5} Midpoint	Week 10 ± 1 week ^{3,5} Endpoint	Early Termination (if applicable) ⁷	Follow Up (30 days [+7] from last Acup tx)
Informed Consent Form	X							
Randomization via CTMS (within 2 weeks from consent)		X ¹²						
Sociodemographics & Medical History (see 5.3.1 and 5.3.2)		X						
Multiple Myeloma status ⁶		X						
ECOG	X							
Height / Weight/ BMI		X						
Acupuncture Expectancy Scale ⁴		X ⁴						
Acupuncture Treatment ^{1,2}			X ²	X ²				
Collect Chemotherapy regimen information ¹⁰	X					X	X	
Adverse Events of Special Interest ⁸			Continuously, starting at First Acupuncture session			X	X ¹³	
CIPN: Neuropathy 0-10 & neuropathy physical location	X ¹¹				X	X	X	
CIPN: FACT-GOG-NTX		X ¹⁴			X	X	X	
Other Symptoms: Constipation, dizziness, dry mouth		X ¹⁴			X	X	X	
Quality of Life: CDC HRQOL-4		X ¹⁴			X	X	X	
Opioid Intake/ Morphine Equivalent Daily Dose (see Appendix B)		X ⁹			X	X	X	
Concomitant Medication: (See Section 5.3.4 for which medications to collect)		X ⁹			X	X	X	

Key to Footnotes

¹ First acupuncture session to occur within 2 weeks of enrollment (date randomized). Acupuncture treatment schedule to start on a Monday or Thursday only.

² Week 1 for subjects on the acupuncture/intervention arm is the week when the first acupuncture session occurs. Window for acupuncture sessions during Week 1 and Week 2 is at least 1 day (minimum) and no more than 8 days (maximum) between visits. Window for sessions during Weeks 3-10 is at least 2 days (minimum) and no more than 9 days (maximum) between visits. During Week 1 and Week 2, if an acupuncture session is missed, it may be made up the following week (there will be 3 sessions that following week). During Weeks 3-10, no sessions will be made up if missed.

³ Questionnaires at Midpoint and Endpoint should still be collected even if subject decides to discontinue the acupuncture sessions but is willing to stay on study. Week 1 for the control group begins at Randomization.

⁴ Acupuncture Expectancy Scale questionnaire to be collected only from subjects on Intervention (Acupuncture) arm at any time AFTER Randomization has occurred, but PRIOR to first acupuncture session.

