⁵ For acupuncture arm, Midpoint occurs at Week 5 ± 1 week from first acupuncture session, with Endpoint occurring at Week 10 ± 1 week from first acupuncture session. For control arm, Midpoint occurs at Week 5 ± 1 week from Randomization with Endpoint occurring at Week 10 ± 1 week from Randomization.

⁶ Collect MM date of diagnosis and staging at Baseline

⁷ If a subject decides or needs to be withdrawn from the study early (all visits and acupuncture assessments, if applicable), but is willing to complete an Early Termination visit, subject will complete assessments a final time, and will be considered Off Study (See section 8.2). Subjects do not need to complete questionnaires if they have done so within the last 2 weeks.

⁸ AESIs should only be collected on subjects randomized to acupuncture arm, beginning with first acupuncture session until 30 days after final acupuncture session.

⁹ For collection of opioid medication intake and concomitant medications, collect what has been taken over the past 7 days.

¹⁰ Collect chemotherapy regimen information throughout the study (if applicable).

¹¹ CIPN Neuropathy 0-10 & neuropathy physical location questionnaire is to be completed the first time **after consenting and prior to any other baseline procedures or assessments** to determine if the subject qualifies for enrollment into the study (see section 7.1.1).

¹² Notify subject of their randomization result.

¹³ Follow Up on AESIs: Can be done over the phone- this follow up for AESIs is only for subjects randomized to Acupuncture treatment arm.

¹⁴ Questionnaire may be completed after consent and prior to or after Randomization

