7. ADDITIONAL INFORMATION ON STUDY PROCEDURES

7.1.1 Screening/Baseline

Subjects will be consented to the trial, and the CIPN Neuropathy 0-10 (and physical location) questionnaire will be administered. Subjects who score <2 on the CIPN Neuropathy 0-10 questionnaire will be a screen failure and will not be randomized or enrolled into the study. If CIPN Neuropathy 0-10 is answered sufficiently for inclusion (score ≥ 2), the rest of the baseline assessments are to be completed within two weeks from consent. Once eligibility is confirmed, subject will be randomized via CTMS to either Acupuncture (intervention arm) or Standard of Care. Subjects will be notified of their randomization result. Those randomized to Intervention Arm will begin acupuncture sessions within two weeks of enrollment.

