11.1.2 Enrollment Date/On Study Date

The date the subject is randomized.

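### Exclusion 7 omits planned non-study acupuncture, although a single session takes a control off study; secondarily, the 30-day washout is not tied to the baseline score

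*Combined protocol and SAP*

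**What the plan says.** **Co-interventions.** Section 3.3, criterion 7, excludes subjects who "Plan to receive Healing Touch or Oncology Massage during study". Criterion 8 looks only at past use: "Have received acupuncture within 30 days prior to enrollment". The Synopsis carries the same two criteria. Neither place mentions a plan to have acupuncture outside the study.

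**Consequence for controls.** Section 4.1 states: "If a subject in the control group has an acupuncture session while enrolled, they will be discontinued from the study", and that assessments stop at that point. Section 11.4 limits the evaluable population, on which all primary and secondary analyses are run, to subjects with both a baseline and a Week 10 neuropathy score.

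**Dates.** Section 11.1.2 defines the enrollment date as "The date the subject is randomized". Footnote 1 of the Study Calendar agrees: "First acupuncture session to occur within 2 weeks of enrollment (date randomized)". The calendar row for randomization reads "Randomization via CTMS (within 2 weeks from consent)".

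**Baseline score.** Section 7.1.1 puts the neuropathy score at consent: "Subjects will be consented to the trial, and the CIPN Neuropathy 0-10 (and physical location) questionnaire will be administered". Footnote 11 says the "CIPN Neuropathy 0-10 & neuropathy physical location questionnaire is to be completed the first time" after consent and ahead of all other baseline procedures. The calendar marks it only under Screening before the Midpoint visit, so this one score decides eligibility (at least 2), the stratum (2–6 or 7–10) and the baseline for the primary endpoint in section 11.3.1.

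**The concern.** The protocol treats outside acupuncture in a control as serious enough to end participation, yet does not ask about it at entry. It does ask about two other planned therapies. A subject who already intends to have acupuncture is therefore eligible. If allocated to control and treated once, that subject leaves the study, and the loss arises from allocation and behavior in one arm only. In the acupuncture arm nothing addresses outside sessions. The intervention-compliant definition in section 11.4 checks outside acupuncture only in controls, and the 0–12 session count covers study attendance.

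The possibility is plausible. Section 5.1 describes group acupuncture as ordinary clinical practice at the institute, and the trial is open-label with no sham.

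The washout raises a separate issue. Its natural purpose is to keep recent acupuncture from affecting the starting score. It is counted to randomization, which can come later than that score. If an earlier course were still acting, the score could be too low. The subject might then miss the entry threshold, fall into the other stratum, or have less room to show a 2-point improvement.

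**Working it through.** **1. Is planned outside acupuncture covered elsewhere?**

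- Criterion 8: past acupuncture only.
- Inclusion 9: ability to understand and comply with study procedures. No section makes abstaining from outside acupuncture a study procedure.
- Exclusion 1: illness, or psychiatric or social circumstances, that limit compliance. Not on point.
- Section 4.1 and the intervention-compliant population: both act after randomization, and the latter serves only sensitivity analyses.

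None screens for a plan at entry.

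**2. Reproducing the stated power.** Inputs from section 11.2: two-sided Fisher exact test, alpha 0.20, proportions 0.10 (control) and 0.35 (acupuncture), 22 and 44 evaluable.

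Power = sum over x = 0..n1 and y = 0..n2 of Bin(x; n1, 0.10) × Bin(y; n2, 0.35), counted where the two-sided Fisher p-value is at most 0.20.

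At 22/44 this gives 0.817, which agrees with the stated figure of at least 80%.

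**3. Room for control losses.** Section 11.2 anticipates 75 enrolled, allocated 2:1:

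- controls = 75 × 1/3 = 25
- margin = 25 − 22 = 3 losses from any cause

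**4. Power if controls fall below 22.** The documents give no rate of outside acupuncture, so the losses are assumptions shown as a range. Section 11.5.1 triggers the analysis at 66 evaluable in total, with no minimum per arm, so both cases are shown.

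| Controls | Power, 44 acupuncture | Power, total held at 66 |
|---|---|---|
| 22 | 0.817 | 0.817 (22/44) |
| 21 | 0.793 | 0.810 (21/45) |
| 20 | 0.794 | 0.793 (20/46) |
| 19 | 0.776 | 0.780 (19/47) |
| 18 | 0.747 | 0.766 (18/48) |

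The slight rise from 21 to 20 controls in the middle column comes from the discreteness of the exact test. One or two controls short costs between 0.817 − 0.810 = 0.007 and 0.817 − 0.793 = 0.024.

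**5. Washout at the baseline score.** Let W be the shortest permitted interval from the last session to randomization, and g the days from the score to randomization (0 to 14). Washout at the score = W − g.

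| g (days) | W = 30 | W = 31 (day 30 itself barred) |
|---|---|---|
| 0 | 30 | 31 |
| 7 | 23 | 24 |
| 14 | 16 | 17 |

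A session between the score and randomization would be at most 14 days before enrollment, so the current text already excludes it.

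**The case against.** **The entry question misses the cases that matter most.** A control who turns to acupuncture in week 4 because symptoms persist may have had no plan at screening. This stands: the change reduces only foreseeable contamination and leaves the section 4.1 rule as it is.

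**Bias.** A reader might infer that removing treated controls inflates the control improvement rate, because those who seek acupuncture are the ones not improving. The documents do not support that as a finding: they say nothing about who would seek it or how many. If it were so, the shift would work against acupuncture and would not create a false positive.

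**Power.** A reader might also infer that the sample size is at risk. The 75 is an estimate, not a cap, the analysis waits for 66 evaluable subjects, and the margin of three controls concerns attrition from any cause. The cost of one or two controls is small, as the table shows.

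**Existing safeguards.** Section 4.1 states the consequence, inclusion 9 gives the enrolling physician some discretion, and calendar footnote 7 offers final assessments to a subject who must be withdrawn early. These soften the problem without closing it. Footnote 7 also sits uneasily with the rule in 4.1 that assessments stop, and a score from an early visit outside the Week 10 window would not make the subject evaluable. The consent form is not in the copy reviewed, so what subjects are told about outside acupuncture is unknown.

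**Acupuncture arm.** Twelve sessions are free, so the incentive for extra ones is weak, and the dose-response analysis is exploratory. This is fair.

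**Washout.** Sixteen days needs the last session at the limit and the full two-week gap. The case series in section 1.1.4 reports lasting relief in two of three patients but gives no duration, so it cannot show that 30 days is enough and 16 is not. A reader might infer bias between arms. The score precedes randomization, so any carry-over should balance on average.

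**Conclusion.** Both gaps are in the text, and both are modest.

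The main one is an inconsistency: the protocol screens for two planned therapies but not for the one that ends a control's participation. It permits an avoidable post-randomization loss in one arm. Its size cannot be derived from the documents. Under the assumed loss of one or two controls below 22, exact power is about 0.79–0.81 instead of 0.817. Neither a direction of bias nor a material threat to the planned power is established.

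The washout point is secondary. The shortest interval before the baseline score is 16 or 17 days, depending on whether day 30 counts, and only at the limit of the permitted gap. It bears on the accuracy of eligibility, stratum and endpoint, and does not suggest a difference between arms.

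Neither point changes the stated sample size, test or endpoint. They call for a cheap improvement in wording.

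**What to change.** 1. Extend exclusion 7, in section 3.3 and the Synopsis, so that it also covers a plan to receive any acupuncture outside the study during participation. Cost: one screening question and a few subjects excluded. This will not prevent decisions made after allocation.

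2. Reconcile exclusion 8 with the timing of the baseline score. One way is to count the stated 30 days back from the screening Neuropathy 0-10 score while still excluding any session between that score and randomization. The second clause is needed once the anchor moves, because such a session would no longer fall inside the 30 days. Cost: some subjects wait up to two more weeks before screening. Make the same edit in the Synopsis.

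3. When making these edits, reconcile the section 4.1 statement that assessments stop with the early-termination assessments in calendar footnote 7, so that staff know what is collected from a discontinued control.

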3.4 Screen Failures

A subject who, for any reason (e.g., failure to satisfy the eligibility criteria or withdraws consent), terminates his/her study participation before randomization is regarded as a “screen failure.” All screen failures will be tracked. Reasons (e.g. specific inclusion/exclusion criteria) for screen failure will be recorded in the dataset.

4. SUBJECT ALLOCATION

4.1 Randomization

Subjects will be randomized in a 2:1 fashion to either acupuncture plus standard subject management or standard of care alone and assigned a Sequence Number. This will be accomplished utilizing the CTMS, whereby a list of Sequence Numbers and associated treatment arm assignments randomly generated prior to study activation will be uploaded by a member of the Levine Cancer Institute Biostatistics Core. The Sequence Number will be a four digit, randomly generated ID number, ranging from 0001 to 9999. A stratified block randomization will be utilized including the following stratification factors to reduce confounding of comparisons between the treatment arms:

- Baseline neuropathy score (neuropathy score 2 – 6 vs 7 – 10)

Blinding will not be possible within this trial because the subjects and study personnel will be able to decipher intervention from control based on the study activities. Those exposed to acupuncture will understand that they are in the intervention group and those given standard of care only will understand that they are in the control group. If a subject in the control group has an acupuncture session while enrolled, they will be discontinued from the study and all further assessments at that point.

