1.1.2 Chemo- Induced Peripheral Neuropathy (CIPN)

First-line treatment for MM is usually bortezomib (Velcade®) or bortezomib combination chemotherapy.³⁻⁵ At Levine Cancer Institute, approximately 85% of MM patients receive bortezomib containing chemotherapy. Although chemotherapy is associated with improved survival, it is neurotoxic and causes CIPN in approximately 30% of patients.^{6,7} CIPN is characterized by sensory symptoms including tingling, numbness, burning, weakness, pain, aching in the hands and/or feet,⁸ and neuropathic pain in more severe cases.⁹ The pathophysiological mechanisms of CIPN are complex and multi-factorial which include oxidative stress, apoptotic mechanisms, altered calcium homeostasis, axon degeneration, membrane remodeling, and neuroinflammation.¹⁰ Bortezomib-induced peripheral neuropathy in MM patients usually presents within the first five cycles of treatment.¹¹

Depending on the severity of CIPN, the dose of bortezomib may be reduced or discontinued to avoid debilitating side-effects. Dose reductions and discontinuation of treatment negatively impact the treatment's ability to prolong life.¹¹ Individuals with CIPN experience reduced quality of life (QOL) due to poor physical function, greater disability, falls, and reduced functioning.¹²⁻¹⁵ CIPN may last for years past treatment and is sometimes permanent.¹⁶

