5.3.2 Medical History

The medical history information to be collected at baseline only, includes:

- Peripheral (sensory) neuropathy Grade by CTCAE 5.0 criteria⁶⁸ (only if recorded in medical record)
- MM diagnosis date and staging
- ECOG performance status⁶⁹
- Body mass index (BMI) calculated by height and weight
- History of diabetes (excluding gestational diabetes)
- Cardiovascular disease
- Chronic kidney disease
- Vertebral fractures

- Current chemotherapy regimen and all bortezomib/bortezomib-combination treatment given prior to enrollment

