11.2 Sample Size

This study is designed with a primary objective to evaluate the effectiveness of acupuncture versus standard subject management in terms of reduction of neuropathy in actively treated multiple myeloma subjects diagnosed with CIPN. A Fisher's Exact Test with a two-sided alpha = 0.20 significance level will have at least 80% power to detect the difference between a standard of care group proportion of 0.10 and a treatment group proportion of 0.35 when the sample sizes are at least 22 and 44 evaluable subjects, respectively. In order to identify at least 66 evaluable subjects, we anticipate enrolling 75 subjects.

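### Bortezomib status at entry is neither a stratification factor nor a forced covariate, so a chance imbalance in it could shift this small trial's estimate in either direction

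*Combined protocol and SAP*

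**What the plan says.** **Who is enrolled.** Section 3.2, criterion 4, admits "Currently being treated with bortezomib or bortezomib-combination chemotherapy OR subjects who have discontinued bortezomib within the past 12 months but continue to have CIPN", with no cap on either group. Section 2.1.1 also names "multiple myeloma subjects who have discontinued bortezomib within the past 12 months but continue to have CIPN" in the primary objective.

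**How they are allocated.** Section 4.1: "Subjects will be randomized in a 2:1 fashion". The stated purpose of stratifying is "to reduce confounding of comparisons between the treatment arms", and the only factor listed is "Baseline neuropathy score (neuropathy score 2 – 6 vs 7 – 10".

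**How the primary endpoint is analysed.** Section 11.5.4 plans a two-sided Fisher exact test on the proportion improving by at least 2 points. It adds a logistic regression for baseline confounders. Candidates enter if significant in univariate models and stay if they survive backward elimination; treatment is then added. Bortezomib status is not named there, and sections 11.5.4 to 11.5.7 plan no summary by status.

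**What is recorded.** Section 5.3.2 collects "Current chemotherapy regimen and all bortezomib/bortezomib-combination treatment given prior to enrollment" at baseline, and the study calendar collects the regimen at screening. Status is therefore known before randomization.

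**Sample size.** Section 11.2 assumes improvement rates of 0.10 and 0.35 with 22 and 44 evaluable subjects at two-sided alpha 0.20. It describes the aim as "in terms of reduction of neuropathy in actively treated multiple myeloma subjects diagnosed with CIPN", as does the synopsis.

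**The concern.** The eligibility criteria define two routes of entry: continuing exposure to a neurotoxic drug, and exposure that ended up to a year earlier. If natural improvement over ten weeks differs between them, status is prognostic. With only 22 controls, the off-drug share can differ noticeably between arms by chance. An unadjusted test does not separate that difference from an acupuncture effect, and a screening rule based on significance can drop a real confounder in 66 subjects.

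At stake are the precision and reading of a single small trial, and whether the 0.10 control rate suits the population actually enrolled.

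**Working it through.** **Inputs from the documents:** 22 controls and 44 acupuncture subjects; rates 0.10 and 0.35; two-sided alpha 0.20 (11.2).

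**Assumed, because the documents give no figure:** 30% or 50% of subjects off bortezomib; improvement without any acupuncture effect of 5% on drug and 15%, 25% or 35% off drug.

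**1. The plan's own figure.** Exact power of the two-sided Fisher test, summed over all 23 × 45 tables at 0.10 vs 0.35, is 81.7%. The stated figure of at least 80% is reproduced.

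**2. Size of chance imbalance.** For an off-drug share q, the SD of the between-arm difference is √[q(1−q)(1/22 + 1/44)].
- q = 0.3: √(0.21 × 0.0682) = 0.120
- q = 0.5: √(0.25 × 0.0682) = 0.131

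Simulated block randomization stratified by score only (assumed block size 6, 30% of subjects in the high-score stratum) gives SDs of 12.0 and 13.0 points. A difference of 20 points or more, in either direction, occurs in 10.0% and 13.1% of trials. Simple hypergeometric allocation gives 8.8% (20 of 66 off drug) and 19.1% (33 of 66). These tail figures are sensitive to the threshold because the difference moves in steps of 1/22 + 1/44 = 6.8 points.

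**3. Effect on the estimate, given an imbalance.** Shift = imbalance × (off-drug rate − on-drug rate). The last column is the exact probability that the Fisher test declares acupuncture better when it has no effect.

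| Off-drug subjects, control vs acupuncture | Imbalance | Rates on / off | Shift | False finding for acupuncture |
|---|---|---|---|---|
| 3/22 vs 17/44 | 25.0 pts | 5% / 15% | 2.5 pts | 8.6% |
| | | 5% / 25% | 5.0 pts | 14.2% |
| | | 5% / 35% | 7.5 pts | 19.8% |
| 8/22 vs 25/44 | 20.5 pts | 5% / 15% | 2.0 pts | 8.1% |
| | | 5% / 25% | 4.1 pts | 11.4% |
| | | 5% / 35% | 6.1 pts | 15.6% |

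The nominal level is 10% per side; with near-balanced arms the actual value is about 4–5%. An excess of 20 points or more in the acupuncture arm specifically has a probability of about 3–10%. The same excess in the control arm shifts the estimate equally far against acupuncture.

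**4. Averaged over all allocations.** Under the same rates the two-sided type I error is 0.12–0.15 against a nominal 0.20, and false findings for acupuncture run at 0.05–0.07 against 0.10.

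**5. Effect of the remedy.** With status added as a stratification factor, the simulated SD falls from 12.0 to 3.7 points (30% off drug) and from 13.0 to 3.5 (50% off). Differences of 15 points or more fall from 22–25% of trials to under 0.1%. Alternatively, a CMH test stratified by status holds the false finding for acupuncture at 0.10 (two-sided 0.20–0.21) under imbalances of 18–25 points with off-drug rates of 25% or 35%. That makes the error independent of the imbalance. It does not keep it at the conservative level that Fisher's test has when the arms are balanced.

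**6. A separate matter: the control rate.** With half off drug and rates of 5% and 35%, the pooled control rate is 0.5 × 5% + 0.5 × 35% = 20%.

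| Control | Acupuncture | Exact power |
|---|---|---|
| 0.10 | 0.35 | 81.7% |
| 0.20 | 0.45 | 76% |
| 0.20 | 0.35 | 44% |

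**The case against.** **A different course by status is not documented.** A reader might infer from section 1.1.2, "Depending on the severity of CIPN, the dose of bortezomib may be reduced or discontinued to avoid debilitating side-effects", that neuropathy recovers once the drug stops. That sentence explains why dosing is changed and gives no recovery rate. The same section says neuropathy can outlast treatment by years or be permanent, and off-drug subjects qualify only if theirs has persisted. This stands: the size of any difference is an assumption.

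**Status at entry is a rough proxy.** Off-drug subjects may have started another neurotoxic therapy (3.2), and on-drug subjects may stop during the study and still be assessed (5.1). This stands, and it argues for the lower end of the range. At 5% on and 15% off, even a 25-point imbalance leaves false findings for acupuncture below the nominal 10%.

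**Randomization already covers chance imbalance.** A reader might infer that the result is biased or the false-positive rate inflated. Step 4 shows that neither holds over repeated randomizations. What remains is conditional: this one trial's estimate may be shifted, in either direction.

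**An adjusted analysis is planned.** It is, and section 11.5.5 allows baseline factors in the repeated-measures model too. It would be wrong to say the plan makes no adjustment. But status is neither named nor forced in, and the regression supplements the primary test.

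**The sample-size wording may be loose.** Section 11.2 does not say that active treatment means bortezomib, so reading 0.10 as an on-bortezomib rate is an inference. The mismatch with sections 2.1.1 and 3.2 remains.

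**Conclusion.** The concern holds as one of chance imbalance and precision. Two entry groups are pooled, a known binary status is left out of a stratification meant to limit confounding, the primary test is unadjusted, and the supplementary regression does not secure adjustment. If 30–50% of subjects are off drug, the imbalance has an SD of about 12–13 points. Under assumed improvement of 5% on and 15–35% off drug, an imbalance of 20–25 points shifts the estimate by about 2–8 points against the 25-point target. If the two groups have the same course, the shift is zero.

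The documents do not support a claim of systematic bias or of overall type I error above nominal. The power loss at a higher control rate comes from the enrolled mix, and stratifying does not change it. The change is worth making because it is cheap; nothing here invalidates the trial.

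**What to change.** 1. **Section 4.1:** add bortezomib status at randomization (currently receiving vs discontinued) as a second stratification factor. Sample size and alpha do not change. The cost is a regenerated list and four strata instead of two, with a few incomplete blocks among 75 subjects. Small blocks in an unblinded single-centre trial make assignments easier to predict, so keep block sizes concealed and preferably varied.
2. **If enrolment has begun:** amend section 11.5.4, before outcomes by arm are examined, to force status into the adjusted logistic model whatever its significance, or to use it as a CMH stratum. The data are already collected under section 5.3.2.
3. **Section 11.5.4:** add one table of improvement rates by arm within status, labelled descriptive. The smaller status group would hold about 22 × 0.3 = 6.6 to 22 × 0.5 = 11 controls, too few to settle whether the effect differs by route of entry.
4. **Section 11.2 and the synopsis:** reconcile the population wording with sections 2.1.1 and 3.2, state that 0.10 is assumed for the enrolled mix, and show power at a control rate of 0.20 (76% for 0.45, 44% for 0.35). This costs only text.
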